1.0 Background

The status quo for the prediction, diagnosis and treatment of VEGFR-TKI and immune checkpoint-inhibitor (ICI) hypertension and vascular disease is application of the consensus guidelines developed for essential hypertension in the general population. In particular, the active surveillance for hypertension and use of common anti-hypertensive medications in cardio-oncology patients is derived from randomized controlled trials of hypertension in adults with the common comorbidities of aging. Notably, cancer patients have been systematically excluded from these trials. As a result, the current approach belies the distinct oncologic context of VEGFR-TKI or ICI use and their toxicities and inherently limits the evidence for applying these guidelines to this unique patient group. Overall, it remains unclear whether prevailing mechanistic concepts to explain essential hypertension or the algorithms for anti-hypertensive medications should be extrapolated to patients with malignancies who are on treatment with anti-angiogenic therapies. For example, human studies of VEGFR-TKI-mediated hypertension have described correlations between specific EC metabolites implicated in blood pressure homeostasis such as nitric oxide or ET-1, but the impact of targeted therapies to interdict these pathways remain untested. Our research disrupts this paradigm by constructing a new precision medicine framework for the clinical approach to this at-risk oncology patient population. *The central innovation in this proposal is that VEGFR-TKI-mediated hypertension stems from context-specific biologic mechanisms determined by medication- and patient-specific variables that can be leveraged for risk prediction and implementation of rational therapies.* An additional advance of this proposal is the establishment of an interdisciplinary team focused on cardio-oncology patients at VUMC to enable an innovative, multi-dimensional research approach spanning basic, clinical/translational and population science.

2.0 Rationale and Specific Aim

We hypothesize that VEGFR-TKIs, ICIs, and combination treatment cause hypertension and vascular dysfunction through ET-1 induction and this pathway is a target for precision therapeutic interventions and novel risk stratification.

[figure not shown]
Aim

VEGFR-TKIs, ICIs, and the combination-mediated increases in ETA receptor activation will cause hypertension and reduce the bioavailability of endothelium-derived nitric oxide. We have previously demonstrated that two structurally distinct VEGFR TKIs reduce the bioavailability of endothelium-derived nitric oxide. We hypothesize that VEGFR TKIs antagonism will reduce digital microvessel hyperemia. As hypertension is mediated primarily in the microvasculature, we anticipate an enhanced response in this vascular bed.

3.0 Animal Studies and Previous Human Studies

VEGFR2 inhibition decreases constitutive nitric oxide bioavailability

We have studied seventeen patients with stage IV breast cancer received who received the VEGFR-TKI vandetanib as part of a phase 1 protocol. We determined blood pressure and systemic NOx concentrations. We further examined endothelial function by measuring the effects of vandetanib on endothelial cell nitric oxide production and Akt473 phosphorylation were examined in vitro.

Vandetanib treatment for 6 weeks significantly increased blood pressure and decreased plasma nitrites and nitrotyrosine, but not a marker of oxidative stress (8-OHDG) compared to baseline (Table).

| Parameter | | Baseline | 6 Weeks | Comparison |
|------------------------------------|---------|----------------|----------------|------------|
| Mean Arterial Pressure | (mm Hg) | 91 +/- 8 | 102 +/- 10 | p = 0.001 |
| Heart Rate | (BPM) | 74 +/- 13 | 71 +/- 10 | p = 0.28 |
| Nitrates/Nitrites (NOx) | (AU) | 48446 ± 1264 | 46799 ± 1740 | p < 0.001 |
| Nitrotyrosine | (AU) | 259814 ± 26139 | 246157 ± 20501 | p = 0.03 |
| 8-hydroxy-2'-deoxyguanosine | (AU) | 1.96 ± 0.09 | 2.0 ± 0.15 | p = 0.5 |

4.0 Inclusion/Exclusion Criteria

Inclusion criteria

- Male or female, age 40 - 75 years old
- Diagnosis of cancer
- Receiving VEGF inhibitor, ICI, or combination (VEGF inhibitor + ICI or combination ICI) treatment, or not receiving any treatment.
- Normal blood pressure or blood pressure treated to < 140/90 mm Hg with ≤2 antihypertensive medications

Exclusion criteria

- Presence of peripheral artery disease
- History of a heart attack within 1 year
- History of a stroke within 1 year
- Diabetes
- Life expectancy < 3 months
- Women who are pregnant
- Women who are nursing

5.0 Enrollment/Randomization

We will study 80 subjects with cancer who will be treated with VEGF inhibitor, ICI, or combination (VEGF inhibitor plus ICI or combination ICI treatment), or not receiving any of the above treatments and will serve as controls. We will restrict enrollment to age 40 - 75 years. Subjects will be identified by research staff from Vanderbilt Ingram Cancer Center (VICC) Clinics. If appropriate, the physician seeing the patient in clinic will approach the patient about participating in a clinical trial and alert the appropriate research staff for further study discussion with the patient. The patient will be consented or be allowed to take the consent form home to read if they are interested. We will use the VUMC Research Derivative, a fully identified clinical database specialized for research, to scan the population of patients in the VUMC electronic health record and use this information to approach patients with renal cell carcinoma, with the participants attending physicians' prior consent. Research coordinators at the Vanderbilt Translational and Clinical Cardiovascular Research Center (VTRACC) have had success in recruiting several thousand subjects in the last 5 years for a variety of projects. In addition to the VTRACC research staff, the study will also utilize services provided by the Vanderbilt Coordinating Center. The VCC will provide nursing support to assist the research coordinators with study procedures, consenting patients, placing the IV catheter, and collection of the endothelial samples.

6.0 Study Procedures

Baseline. We will recruit subjects who have not yet begun their treatment. The subjects most recent labs will be reviewed by study staff as part of the screening process. Subjects will report to the Preston Research Building after a \geq 5 hour fast. First an informed consent will be obtained (if not already obtained during the patient's clinic visit), followed by a medical history, an abbreviated physical exam, and taking the subjects weight. After the patient has been sitting for 10 minutes, blood pressure will be measured in triplicate using an automated oscillometric device, baseline and hyperemic velocity time interval (VTI), and digital pulse amplitude tonometry will be performed to measure the reactive hyperemia index. We will draw blood for renal function, sodium and potassium, fasting glucose and insulin, metabolics, markers of inflammation, and markers of oxidative stress. We will measure urinary albumin/creatinine ratio (UACR). We will place an IV catheter for blood sampling and endothelial cell harvest. Endothelial cells (ECs) will be harvested from patients for gene expression (PCR, RNA-sequencing), staining and ATAC assays. Subjects will then have an ambulatory blood pressure monitor (Spacelabs) placed for 24 hours.

Follow-up Visit Approximately 1 month after starting treatment, subjects will return to the Preston Research Building. The procedures will be the same as the baseline visit procedures. We will start by discussing changes to medical history since the beginning of the study, conduct an abbreviated physical exam, and take the subjects weight. After the patient has been sitting for 10 minutes, blood pressure will be measured in triplicate using an automated oscillometric device, baseline and hyperemic velocity time interval (VTI), and digital pulse amplitude tonometry will be performed to measure the reactive hyperemia index. We will draw blood for renal function, sodium and potassium, fasting glucose and insulin, metabolics, markers of inflammation, and markers of oxidative stress. We will measure urinary albumin/creatinine ratio (UACR). We will place an IV catheter for blood sampling and endothelial cell harvest. Endothelial cells (ECs) will be harvested from patients for gene expression (PCR, RNA-sequencing), staining and ATAC assays. Subjects will then have an ambulatory blood pressure monitor (Spacelabs) placed for 24 hours.

Standard Techniques

Peripheral Artery Tonometry Digital pulse amplitude will be measured in the fasting state with a peripheral artery tonometry (PAT) device placed on the tip of each index finger (Endo-PAT2000, Itamar Medical, Caesarea, Israel). The PAT device comprises a pneumatic plethysmograph that applies uniform pressure to the surface of the distal finger, allowing measurement of pulse volume changes in the finger. Throughout the study, the inflation pressure of the digital device is electronically set to 10 mm Hg below diastolic blood pressure or 70 mm Hg (whichever is lower). Baseline pulse amplitude is measured from each fingertip for 2 minutes 20 seconds. Arterial flow is arrested for 5 minutes by a cuff placed on a proximal forearm (Hokanson AG101, D.E. Hokanson Inc, Bellevue, WA) at whichever occlusion pressure would be higher: 200 mm Hg or 60 mm Hg plus systolic blood pressure. Pulse amplitude is recorded electronically in both fingers and analyzed by a computerized, automated algorithm (Itamar Medical) that provides the average pulse amplitude for each 30-second interval after forearm cuff deflation up to 4 minutes. To determine the PAT ratio, we will first calculate the ratio of the post-deflation pulse amplitude to the baseline pulse amplitude in the 90- to 120-second postdeflation time period (ie, $X_{h90-120}/X_{h0}$: with h denoting hyperemic finger and 0 denoting baseline, X being the pulse amplitude). Then, we divided this result by the corresponding ratio from the contralateral, control hand (ie, $X_{c90-120}/X_{c0}$: with c denoting the control finger and 0 denoting baseline) to obtain the PAT ratio. Because PAT ratio has a heteroscedastic error structure, we use natural logarithm transformation in all analyses such that PAT ratio= $\ln[(X_{h90-120}/X_{h0})/(X_{c90-120}/X_{c0})]$.

Endothelial cell harvest The Brown and [name] Laboratories have developed a novel technique based on a protocol for isolation of ECs and leukocytes directly from the cubital veins of human subjects¹. This procedure involves gentle scraping of the vein using a 0.014" j-wire followed by selection of ECs (from red blood cells and leukocytes) using VE-cadherin magnetic beads and rapid sorting by gravity flow (MACS). The cell yields using this technique range from 500-1000. Immunofluorescence of fixed cells demonstrates positive staining for EC markers including von Willebrand factor and no staining for pan-leukocyte marker CD45. Unbiased RNA-sequencing confirms the transcriptomes cluster perfectly by cell type (Figure 6). Further, functional enrichment analysis (ToppGene) reveals differential expression of genes associated with cell type specific functions. Importantly for this proposal, these patient-specific ECs express genes of the endothelin-1 and VEGF signaling pathways including EDN1. This novel technique enables us to test the effects of VEGFR-TKI, ICI, and the combination of agents in the vasculature directly from humans for the first time.

For these experiments, we will isolate ECs from patients before and after starting VEGFR-TKI, ICI, and combination therapy (on treatment, approximately 30 days). EC preparations will be divided for the following: a) RNA extraction to measure expression of relevant genes involved in both VEGF and ET-1 pathways including FLT1, FLK1, FLT4, EDN1, ETRB and endothelin converting enzyme (ECE); b) isolation of nuclei to perform ATAC-seq with the goal of mapping the regulatory elements in patient-derived ECs. ATAC data are strongly correlated with enhancer maps generated with ChIP datasets². However, the lower cell yield renders conventional ChIP assays challenging. As such, ATAC assays will be used to provide specific insight into enhancer architecture. We will integrate ATAC data with gene expression data from

patient ECs to determine the effects of VEGFR-TKI, ICI, or the combination of agents on the EC epigenome *in vivo* in humans.

BP Measurements At baseline and the follow-up visit outpatient BP will be measured with an aneroid sphygmomanometer (Welch Allyn, Skaneateles Falls, NY), using the appearance and complete disappearance of the Korotkoff sounds (K1 and K5) as SBP and DBP. The mean of three seated measurements, performed two minutes apart, will be used. During study days, BP will be measured using an automated oscillometric recording device (Dinamap, Critikon, Carlsbad, CA) and will be completed with the subjects sitting. Ambulatory BP monitoring will be performed with a portable noninvasive recorder (SpaceLabs Inc., Redmond, WA) for 24-consecutive hours at the end of the baseline and follow up study visits.

Laboratory Testing The following biomarker measurements will be done in collaboration with [name] [name] in the Vanderbilt Cardiology Core lab. Her lab has extensive experience working with ELISA-based biomarker detection, and offers these tests as routine service. Plasma aldosterone level will be tested using Aldosterone ELISA kit (Eagle Biosciences, Cat# DCM053-8). Based on the manufacturer's data, the intraassay variation is $\leq 9.7\%$ and the inter assay variation is $\leq 11\%$, respectively. The Vascular Endothelial Growth Factor 165B (VEGF-165B) will be tested using quantitative sandwich ELISA kit from MyBiosource (Cat# MBS109074). The sensitivity of this kit is 5.0 pg/ml and both Intra-assay CV (%) and Inter-assay CV (%) is less than 15%. Human Serum Adipokines (HGF, Leptin, IL-1 β , IL-6 IL-8/CXCL8, Insulin, MCP-1/CCL2, NGF and TNF- α) will be measured using EMD Millipore/Sigma Milliplex Map Human Adipokine Magnetic Bead Panel 1 (Millipore/Sigma, Cat# HADK1MAG-61K) according to manufacturer's instructions. The Cardiology Core lab has Luminex 200 and is well set up to run these types of assays as their routine service. We will run F2-isoprostanes using mass spectrometric methods developed at Vanderbilt.

Type and Amount Of Sample Needed: About 40 mL and about 10 mL of urine at each of the study visits.

7.0 Risks

Phlebotomy: drawing blood may cause pain, bruising, lightheadedness and rarely, infection.

Intravenous catheter placement: common risks include pain at the site of the needle stick and mild bruising. Uncommon risks are hematoma, infection, and phlebitis.

Endothelial biopsy: there are not any common risks. An uncommon risk is phlebitis.

8.0 Reporting of Adverse Events or Unanticipated Problems involving Risk to Participants or Others

Adverse events will be reported the IRB per Vanderbilt University IRB Policy.

9.0 Study Withdrawal/Discontinuation

Subjects may withdraw consent for study participation at any time by informing the PI.

10.0 Statistical Considerations

Power: Hypertension: In studies of TKI, ICI, and the combination use, increases in blood pressure begin within days and reach steady state over weeks. Pazopanib has been shown to increase mean arterial blood pressure by 15 mm Hg in this time frame^{3,4}. Based on the previous studies, we assume the mean changes of BP is 15 mm Hg, with a standard deviation of 10 mm Hg. We first conducted power analysis with ANOVA framework. With will have 100% power to detect a difference of 8 mm Hg. Our power analysis is conservative because the standard deviation of BP should be much less than 10 mm Hg.

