Novel Mechanisms and Predictors of VEGF Receptor Inhibitor- or Immune Checkpoint Inhibitor-Associated Hypertension and Cardiovascular Disease

NCT03709771

Date: October 30, 2018

Sample Size and Power Calculation:

Hypertension: In studies of TKI use, increases in blood pressure begin within days and reach steady state over weeks. Pazopanib has been shown to increase mean arterial blood pressure by 15 mm Hg in this time frame^{75,76}. Based on the previous studies, we assume it is reasonable to expect the mean changes of BP for placebo group is 15 mm Hg, the mean changes of BP for bosentan group is 7 mm Hg, the mean changes of BP for the ambrisentan group is 0 mm Hg, all with a standard deviation of 10 mm Hg. We first conducted power analysis with ANOVA framework. We planned to recruit 45 patients per group. In power calculation, to account for potential loss-to-follow issue that happens in almost every longitudinal studies, we considered 40 patients per group. With 40 subjects per group, we will have 100% power to detect whether there is any significant differences among three study arms. When comparing ambrisentan group to the placebo, with 40 subjects per group, we will have 100% power to detect whether there is significant difference between two groups. To be conservative, we set the mean changes of BP for placebo group to 12 mm Hg, the mean changes of BP for bosentan group to 6mm Hg. The analysis showed we still have 99.8% power to detect whether there is significant difference between groups.

We also evaluated the required minimum detectable effect size with 40 subjects per group to achieve 80% power. As can be seen from Figure 8, the minimum detectable effect size (f) required is about 0.29 (i.e., 7.7% of the total variance accounted for by groups). Although this is considered a medium effect size (f=0.25, Cohen, 1988), it is much smaller than the effect size we expected (f=0.61).

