When comparing bosentan group to the placebo, with 40 subjects per group, we will have 86.8% power to detect whether there is significant difference between two groups. Significant level was set at 0.05/3 to account for multiple comparison. Once again, we evaluated the required minimum detectable effect size with 40 subjects per group to achieve 80% power. The results showed that the required minimum detectable effect size is $d=0.74$, which means the minimum detectable difference between placebo and bosentan group is 7.4. Although this is considered a large effect size ($d=0.8$, Cohen, 1988), we are confident in observing this difference based on previous studies.

Our power analysis is conservative because first the standard deviation of BP changes in placebo group should be much less than 10 mm Hg; Second, the power achieved in analysis of covariance (ANCOVA) is higher than that in ANOVA because the residual variance in ANCOVA is minimized.

[figure not shown]
FMD: In studies of VEGFR-TKI inhibitors, worsening in endothelial function is proportionate to the increase in blood pressure. Based on our previous work, we anticipate a $3\% \pm 4\%$ decrease in brachial artery FMD in subjects treated with placebo⁴⁴. Bosentan has previously been shown to improve endothelial function in hypertension⁷⁷, and we anticipate greater vascular function effects with ambrisentan. Like blood pressure outcome, we evaluated the required minimum detectable effect size with 40 subjects per group to achieve 80% power. Once again, as can be seen from Figure 8, the minimum detectable effect size (f) required is about 0.29. This is considered a medium effect size (f=0.25, Cohen, 1988) and we are confident in observing this effect size for FMD outcome based on previous studies.

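### The protocol's claim of 100% power for 8 mm Hg does not hold for an unadjusted group comparison with 80 patients and SD 10 mm Hg (at most 94%), and its claim that the SD is conservative has no support

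*Protocol*

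**What the plan says.** Protocol section 10.0 is the protocol's only sample-size justification. It assumes a mean blood pressure change of 15 mm Hg with SD 10 mm Hg, refers to ANOVA, and concludes: "With will have 100% power to detect a difference of 8 mm Hg". It then adds: "Our power analysis is conservative because the standard deviation of BP should be much less than 10 mm Hg". It does not state which groups are compared, how many patients are in each, or the significance level.

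Section 5.0 supplies the total: "We will study 80 subjects with cancer". These are patients on a VEGF inhibitor, an ICI or a combination, "or not receiving any of the above treatments and will serve as controls". No allocation is given.

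The SAP describes different arms (placebo, bosentan, ambrisentan) but uses the same SD of 10 mm Hg. It expects a change of 15 mm Hg on placebo and 0 on ambrisentan, and for that 15 mm Hg gap says: "When comparing ambrisentan group to the placebo, with 40 subjects per group, we will have 100% power". It also states that "the mean changes of BP for bosentan group is 7 mm Hg", which is 8 mm Hg below placebo. For that gap it says: "When comparing bosentan group to the placebo, with 40 subjects per group, we will have 86.8% power", with the qualification "Significant level was set at 0.05/3 to account for multiple comparison". Its Data Analysis Plan is an ANCOVA comparing arms, adjusted for baseline blood pressure.

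**The concern.** An 8 mm Hg difference against an SD of 10 mm Hg is a standardised difference of 0.8. With 80 patients in total, that is not detected with near certainty in a group comparison, and the SAP's figure for the same difference is well short of 100%. In the SAP, 100% belongs to the 15 mm Hg gap and to the three-arm overall test.

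A reader of section 10.0 would conclude that a true 8 mm Hg difference would almost never be missed, and might read a null result as strong evidence against one. Because no contrast is named, the reader also cannot tell which comparison the 80 patients were chosen for. The SD sentence adds to this by suggesting that the real power is higher still.

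**Working it through.** **Inputs.** Difference 8 mm Hg and SD 10 mm Hg (protocol 10.0). Total 80 (protocol 5.0). Assumptions, because the protocol is silent: two-sided alpha 0.05, no dropout, and the group sizes shown. Four equal groups of 20 would follow from four categories, but the text does not state them.

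**Method.** For two groups, the noncentrality is δ = difference / (SD × √(1/n₁ + 1/n₂)). Power is the probability that a noncentral t with n₁ + n₂ − 2 degrees of freedom exceeds the critical value. For a k-group ANOVA with n per group, λ = n × Σ(mean − grand mean)² / SD², with power from the noncentral F.

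**1. The SAP's figures reproduce.** SD 10, 40 per group:
- 15 v 7 at 0.05/3: δ = 8 / (10 × √(2/40)) = 8 / 2.236 = 3.58; power 86.8% (SAP: 86.8%).
- 15 v 0 at 0.05/3: δ = 15 / 2.236 = 6.71; power above 99.99% (SAP: 100%).
- Three arms, 15/7/0, at 0.05: power above 99.99% (SAP: 100%).

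**2. The protocol's figure does not reproduce.** Unadjusted comparison, 8 mm Hg, SD 10:

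| Split | δ | Power, two-sided 0.05 | Power, 0.05/3 | Power, one-sided 0.05 |
|---|---|---|---|---|
| 20 v 20 | 8/3.162 = 2.53 | 69.3% | 51.6% | 79.9% |
| 20 v 60 | 8/2.582 = 3.10 | 86.4% | 74.1% | 92.3% |
| 40 v 40 | 8/2.236 = 3.58 | 94.2% | 86.8% | 97.1% |

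40 v 40 is the best of all two-group splits of 80. The difference detectable with 80% power at two-sided 0.05 is 9.1 mm Hg (20 v 20) or 7.3 mm Hg (20 v 60).

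Four-group ANOVA, 20 per group, largest gap 8 mm Hg:
- means 8/4/4/0: λ = 20 × 32/100 = 6.4, power 52%
- means 8/0/0/0: λ = 20 × 48/100 = 9.6, power 72%
- means 8/8/0/0: λ = 20 × 64/100 = 12.8, power 85%

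**3. Where about 100% does arise.**
- Pre-post change of 8 mm Hg, change SD 10, δ = 0.8 × √n: n = 20 gives 92.4%, n = 40 gives 99.85%, n = 60 gives more than 99.99%.
- Group difference of 15 mm Hg, 20 v 20: 99.6%.
- A smaller SD: 99.5% power for 8 mm Hg needs a residual SD of about 5.4 (20 v 20), 6.7 (20 v 60) or 7.8 (40 v 40).

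**4. Baseline adjustment.** If baseline and follow-up SDs are equal, with correlation r and change SD 10, the ANCOVA residual SD is 10 × √((1 + r)/2). Two-sided 0.05:

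| r (assumed) | Residual SD | 20 v 20 | 20 v 60 | 40 v 40 |
|---|---|---|---|---|
| 0.3 | 8.06 | 86% | 97% | 99.2% |
| 0.5 | 8.66 | 81% | 94% | 98.3% |
| 0.7 | 9.22 | 76% | 91% | 96.9% |

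**5. The SD statement.** Section 10.0 gives no figure or source. The SAP makes the assertion only for blood pressure changes in its placebo group, which this protocol does not have. The only variability data are in protocol section 3.0 (17 patients on vandetanib): mean arterial pressure 91 (SD 8) at baseline and 102 (SD 10) at 6 weeks, p = 0.001. If that test was paired, t on 16 degrees of freedom is 4.015, and the change SD is 11 × √17 / 4.015 = 11.3 (95% interval 8.4 to 17.2). An unpaired test on the same summaries gives p = 0.0012, so pairing is not established. From SDs of 8 and 10, the change SD is √(164 − 160r): 10.8, 9.2 or 7.2 at r = 0.3, 0.5 or 0.7. The data neither show an SD much below 10 nor rule it out.

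**The case against.** The strongest reply is that a pre-post test was meant. Section 10.0 assumes a single mean change, and sections 6.0 and 9.0 aside, the visits are before and about one month after treatment starts. For a pooled change of 8 mm Hg in 40 or more patients, 100% is right after rounding. That stands as a possible reading, but the text names ANOVA, the protocol enrols controls, and the SAP's analysis compares arms. A pre-post test would make no use of the controls. If it was meant, the section must say so.

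Second, the planned ANCOVA raises power, to 99.2% for 40 v 40 at r = 0.3. So the 94% ceiling applies to unadjusted tests only. Section 10.0 mentions no adjustment, however, and with 20 v 20 or 20 v 60 adjusted power stays at 76 to 97% over the correlations tried.

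Third, the group sizes and alpha are assumptions. This is true of the 69% and 86%. It does not affect the ceiling over all two-group splits, which stays below 100% even at one-sided 0.05 (97.1%). Nor does it affect the contrast with the SAP's 86.8%.

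Fourth, the SAP's figure comes from a design with other arms. That is also true, and the mismatch is a problem in itself, but the calculation depends only on the difference, SD, group sizes and alpha.

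Last, if the groups really differ by the assumed 15 mm Hg, power is high (99.6% for 20 v 20). The protocol's sentence, however, claims it for 8 mm Hg.

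**Conclusion.** The concern holds. Read as the group comparison that its ANOVA wording and control group imply, the 100% figure is wrong. It overstates power by at least 6 percentage points at the best split, and by about 14 (20 v 60) or 31 (20 v 20) if the groups fall that way. Put differently, a true 8 mm Hg difference would be missed about 14% or 31% of the time in those two cases. These figures rest on SD 10, two-sided 0.05, no covariate adjustment and no dropout; the two smaller splits are assumptions. Adjustment narrows the gap by an amount that depends on an unstated correlation.

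The SD sentence is unsupported, which is not the same as false: the documents leave the change SD open on either side of 10 mm Hg. This should be fixed, but it does not in itself call for a different sample size.

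**What to change.** In protocol section 10.0, name the powered contrast, the expected group sizes and alpha, and replace 100% with the power that follows. Two examples, depending on what is expected:

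- *With 20 patients in each of two groups, SD 10 mm Hg and two-sided alpha 0.05, power is 69% for a difference of 8 mm Hg; 80% power corresponds to 9.1 mm Hg.*
- *With 20 controls and 60 treated patients, SD 10 mm Hg and two-sided alpha 0.05, power is 86% for a difference of 8 mm Hg; 80% power corresponds to 7.3 mm Hg.*

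If a pre-post test was intended, say so and give the number of patients pooled. If the power relies on ANCOVA, state the assumed baseline correlation. Delete the sentence calling the analysis conservative, or support it with an observed SD of change and its source.

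The cost is wording only, with no added patients or procedures. The stated power will look less favourable.

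### The plan calls an SD of 10 mm Hg conservative without data; the sponsor's own pilot makes it a realistic value, and the stated 100% power for 8 mm Hg has no slack behind it

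*Protocol*

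**What the plan says.** Protocol section 10.0 sets the planning values: "we assume the mean changes of BP is 15 mm Hg, with a standard deviation of 10 mm Hg". The 15 is attributed to cited pazopanib studies ("Pazopanib has been shown to increase mean arterial blood pressure by 15 mm Hg in this time frame"). The section then gives the method ("We first conducted power analysis with ANOVA framework") and the result ("With will have 100% power to detect a difference of 8 mm Hg"), and closes with the reassurance: "Our power analysis is conservative because the standard deviation of BP should be much less than 10 mm Hg". It gives no significance level, number of groups or group sizes. Section 5.0 gives only a total ("We will study 80 subjects with cancer who will be treated with VEGF inhibitor, ICI, or combination", plus untreated controls).

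The SAP, under Sample Size and Power Calculation, offers two reasons for calling its power analysis conservative. The first is that "the standard deviation of BP changes in placebo group should be much less than 10 mm Hg". The second is that ANCOVA has more power than ANOVA. Its Data Analysis Plan does specify ANCOVA adjusted for baseline BP.

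Protocol section 3.0 reports the sponsor's pilot: 17 patients with stage IV breast cancer, before and 6 weeks into the VEGFR-TKI vandetanib. The row for mean arterial pressure (MAP) reads "91 +/- 8 | 102 +/- 10 | p = 0.001".

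**The concern.** A planning SD is conservative only if there is reason to expect a smaller one. Neither document cites a source or shows data for a smaller SD, and the one table that bears on the matter points the other way. The pilot is close to the trial's own setting: cancer patients measured before and some weeks after starting a VEGFR-TKI. Section 10.0 does not mention it.

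At stake is what a reader may conclude from the power statement. Someone told that power is 100%, and that even this is cautious, will take a small or absent group difference as firm evidence. If the SD is 10 or a little more and 80 subjects are divided among several groups, that confidence is not warranted.

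**Working it through.** **Inputs.** Protocol section 10.0: difference 8 mm Hg, SD 10. Section 5.0: 80 subjects in total. Section 3.0: n = 17, MAP 91 (SD 8) to 102 (SD 10), p = 0.001. Assumed because the protocol is silent: two-sided 0.05 and the group splits.

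**1. The plan's own figure.** Power was computed from the noncentral t, with noncentrality 8 / [10 × √(1/n₁ + 1/n₂)], or from the noncentral F for four groups of 20.

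| Comparison at SD 10 | Power for 8 mm Hg |
|---|---|
| 40 v 40 | 94% |
| 60 v 20 | 86% |
| 20 v 20 | 69% |
| Four-group ANOVA, 20 each, means 0/8/8/8 | 72% |
| Four-group ANOVA, 20 each, means 0/0/8/8 | 85% |
| Before-after test, all 80 pooled | about 100% |

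The stated 100% is reproduced only by a pooled before-after test, not by any of these between-group comparisons. The same method does reproduce the SAP's three-arm figures: 86.8% for 8 mm Hg with 40 per arm at 0.05/3 (stated 86.8%), and 99.9% for means 12/6/0 (stated 99.8%).

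**2. SD of BP level in the pilot.** Read directly from the table, it is 8 and 10. The on-treatment value equals the planning value.

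**3. SD of BP change in the pilot.**
- Rise: 102 − 91 = 11 mm Hg.
- Paired t on 16 df at p = 0.001: t = 4.015.
- SD of change: 11 × √17 / 4.015 = 11.3.
- If p was rounded from between 0.0005 and 0.0015: 10.4 to 11.9. If the rise could also be 10 to 12: 9.5 to 12.9.
- Sampling 95% CI for 11.3 (chi-square, 16 df): 8.4 to 17.2.
- 95% CI for the rise: 11 ± 2.12 × 11.3/√17 = 5.2 to 16.8.

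In reverse, under a paired t-test with n = 17, an SD of change of 8 would have given p = 0.00003, 9 would have given 0.0001, and 10 would have given 0.0003.

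**4. Is the table paired?** No test is named. Unpaired tests on the other rows give p = 0.003 for NOx (reported < 0.001), 0.10 for nitrotyrosine (reported 0.03) and 0.46 for heart rate (reported 0.28). Those three rows fit a paired analysis and not an unpaired one. The MAP row alone fits either (unpaired p = 0.0012), and the 8-OHDG row does not help.

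**5. What this does to power.**
- Within-person correlation implied by 11.3: r = (8² + 10² − 11.3²) / (2 × 8 × 10) = 0.23.
- Residual SD of follow-up BP given baseline: 10 × √(1 − 0.23²) = 9.7.

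| Split | SD 10 | Unadjusted change, SD 11.3 | Baseline-adjusted, residual SD 9.7 |
|---|---|---|---|
| 40 v 40 | 94% | 88% | 95% |
| 60 v 20 | 86% | 77% | 88% |
| 20 v 20 | 69% | 59% | 72% |

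The last column uses the same noncentral t formula and ignores the few degrees of freedom spent on covariates.

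**The case against.** The strongest reply is that the SAP will not analyse raw change scores. With ANCOVA on baseline BP, the relevant SD on the pilot data is about 9.7, and with a follow-up SD of 10 it cannot exceed 10 whatever the correlation, rounding aside. This stands. The power loss at SD 11.3 applies only to an unadjusted comparison of changes, and the SAP's ANCOVA reason should stay. But 9.7 is not much less than 10 either, so the reply does not rescue the SD reason.

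Second, 11.3 depends on an unnamed test and an unstated number of patients at 6 weeks. With 14 pairs, the paired t would give about 9.8. A paired Wilcoxon test with normal approximation would make p = 0.001 most compatible with an SD near 9; the exact version points to about 10 to 11. This also stands: the p-value does not fix the SD. A reader might infer that the pilot shows the SD to be above 10. It does not, and the interval of 8.4 to 17.2 includes values below 10.

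Third, a reader might infer that the pilot's 11 mm Hg rise refutes the assumed 15. It does not. Its interval of about 5 to 17 includes 15, the drug and the time point differ from those behind the 15, and the 15 does not enter the protocol's power sentence, which concerns 8. The SAP also repeats its calculation with a rise of 12.

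Finally, a wrong planning SD does not bias the final estimates, since the confidence intervals will use the observed variance. That is true, and it limits the matter to what the plan claims about its power.

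**Conclusion.** The point holds as one about an unsupported claim. The SD reason for calling the analysis conservative has no data behind it in either document, and the only BP variability data in them (8 and 10 for level, about 11.3 for change, about 9.7 after baseline adjustment) make 10 realistic rather than cautious. The figure of 11.3 assumes a paired t-test on all 17 patients; the SDs of level need no such assumption.

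The larger numerical gap lies in the power itself. Even at SD 10, the between-group comparisons examined reach 69% to 94%, not 100%. These figures rest on two-sided 0.05 and on assumed splits of 80. The further loss of roughly 6 to 10 percentage points at SD 11.3 is confined to unadjusted change scores; under the planned ANCOVA, power stays close to the SD 10 figures.

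**What to change.** - In protocol section 10.0 and in the SAP's Sample Size and Power Calculation, delete the statement that the SD should be well below 10. Keep the SAP's separate ANCOVA reason. Alternatively, support the statement with the SD of change computed directly from patient-level pilot data, if these are held, naming the test and the number of pairs.
- Replace the 100% figure with power and detectable difference for the actual groups and their sizes, over SDs of 8 to 12, at a stated significance level and for the analysis that will be used. If a pooled before-after comparison is what was meant, say so.

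The cost is wording and a short table. The stated power will look less favourable. No extra patients or procedures are needed.
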